7.5 Efficacy Sensitivity Analysis

8 SAFETY ANALYSES

8.1 General

The safety population will be used for all safety analyses and safety summaries will be presented by treatment group unless otherwise stated. All tables will have a corresponding listing including all patients randomized.

8.2 Duration of Exposure to Test Article and Compliance

Exposure summary by treatment group will be presented for the safety, micro-ITT, and CE-PTE populations.

Duration of exposure to test article (days) for the individual subject is the number of days subject received test article (last day of study test article – first day of test article + 1). Duration of treatment (days) will be summarized using descriptive statistics. The distribution of subjects by the total number of days on test article (1-3, 4-5, 6-7, and > 7 days) will be presented.

The degree of test article compliance will be determined by presenting the number of tablets taken as a percentage of the number required by the protocol.

$$\%Compliance = 100\% * \frac{\text{Actual number of tablets taken}}{\text{Expected \#of tablets}}$$

The last dose date is the last day the subject is expected to receive test article based on the length of therapy determined by the investigator or the actual last date the subject took test article, if s/he prematurely discontinued test article. For subjects who complete the study, the last dose day used in the denominator calculation will be the last expected dosing day. For early termination subjects, the last day of study drug used in the denominator calculation will be the last expected dosing day before termination day. A subject is expected to receive a total of 38 tablets during the treatment phase for subjects enrolled at the time preceding protocol amendment 2, and 56 tablets with amendment 2. For detail on dosing schedules refer to Table 2 of the study protocol.

Descriptive statistics for treatment and fasting compliance will be presented by treatment group and by protocol version at which a subject entered the study.

Number of subjects and percentage with a compliance $\geq 80\%$ will be presented. A summary of compliance with the pre- and post-dose fasting requirements will also be provided. The percent fasting compliance will be determined based on the total doses taken where fasting is required. The percentage of subjects who were < 50%, 50% to < 80%, and 80% to 100% compliance with the pre-dose and post-dose fasting requirements met will be summarized.

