8.17 Subject Discontinuation or Withdrawal

Reasons why a subject may discontinue or be withdrawn from the study include, but are not limited to, AE, lost to follow up, withdrawal by subject, physician decision, death, and other (specify reason eg, subject non-compliance or study termination by the sponsor). Subjects may voluntarily withdraw from the study for any reason at any time. Subjects are considered withdrawn from the study if they state an intention to withdraw, or fail to return for visits, or become lost to follow up for any other reason. If premature withdrawal from the study occurs for any reason, the investigator should determine the primary reason for a subject's premature withdrawal from the study and record this information on the eCRF.

Subjects who discontinue study treatment should not be considered withdrawn from the study (unless the subject withdraws informed consent). The date and primary reason for

discontinuation of study treatment should be recorded. Subjects who discontinue study treatment prematurely should complete the EOT visit, PTE visit and Final Follow-up Assessment, if possible (see Schedule of Events - [Appendix 1](#)). The site should also collect subject safety information through the Final Follow-up assessment.

Site personnel should also contact the IxRS to register the subject's discontinuation from test article.

For subjects who are lost to follow up, the investigator should show "due diligence" by documenting in the source documents steps taken to contact the subject, eg, dates of telephone calls, registered letters, etc.

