10 STUDY SUSPENSION, TERMINATION, AND COMPLETION

10.1 Study Completion and Post-Study Test Article

A subject will have successfully completed the study after the planned test article regimen has been administered, and all assessments and visits have been performed up through the final follow-up assessment (Final Follow-up). The study will be completed when the last subject has either discontinued or completed the Final Follow-up assessment.

No long-term follow-up of subjects is planned, with the exception of pregnancies, as described in [Section 8.15.6](#), and SAEs described in [Section 8.15.1](#).

Sites will be notified by either the Sponsor or IxRS to stop enrollment when the desired number of treated subjects have been enrolled. Subjects already consented, but not yet randomized will be allowed to continue Screening procedures.

Upon study completion, the investigator will provide the sponsor, IRB/IEC/REB, and regulatory agency with final reports and summaries as required by regulations. The investigator must submit a written report to the sponsor and the IRB/IEC/REB within 3 months after the completion or termination of the study.

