4.4 Clinically Evaluable Population

The clinically evaluable (CE) population will consist of all ITT subjects who received test article, have a qualifying infection, an assessment of outcome, and meet all other evaluability criteria as described below.

Inclusion into the CE populations will be determined programmatically based on the data on the electronic case report form (eCRF) and a manual review by the Sponsor as necessary prior to unblinding. Details on allocation to each CE population are described in the [Pathogen and CE Review Plan: PTK0796-uUTI-17201²](#).

Since patient count may differ depending on timepoint, CE populations will be defined by milestone visit (CE-EOT, CE-PTE and CE-FFU).

To be included in the CE populations, subjects must meet all criteria defined below:

1. Qualifying infection:

- Exclusion Criterion #2, 3, and 4; Note: for subjects randomized after amendment 1 or later exclusions 3 and 4 are not applicable.

2. Assessment of outcome for CE population:

Subjects must meet all of the following to be included in any CE populations:

- Subject did not meet any of the exclusion criteria 1 and 7 through 10 in the protocol (Baseline event exclusion).
- Received the randomized test article and was at least 80% compliant with the dosing regimen (Compliance to test article intake).
- Study personnel involved in the assessment of efficacy remained blinded to study treatment, unless a treatment limiting AE occurred that required emergency unblinding.

In addition, for each endpoint the following needs to be satisfied, as appropriate:

a. For the CE-EOT population:

- i. Completed the investigator's assessment of clinical response (ie, was not deemed an indeterminate outcome) at the EOT visit

- ii. The EOT visit occurred on the day of, or within +2 days following the last dose of test article (3-day window).
- b. For the CE-PTE population:
 - i. The Overall Clinical Response (based on the investigator's assessment) at the PTE Visit is not Indeterminate (see [Table 5](#))
 - ii. The PTE Visit occurred on Day 14 (\pm 2 days) after the subject's first dose of test article, unless the subject was considered to be a Clinical Failure based on the investigator's assessment at the EOT visit.
- c. For the CE-FFU population:
 - i. The Overall (Sustained) Clinical Response (based on the investigator's assessment) at the FFU Visit is not Indeterminate (see [Table 6](#))

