Evaluable failure: The subject received at least 3 doses of active test article (omadacycline groups 1, 2, and 3) or at least 4 doses of active test article (nitrofurantoin and omadacycline group 4) and the investigator classifies the subject as a Clinical Failure at the EOT Visit (CE EOT population) or the overall Clinical Response (based on the investigator's assessment) at the PTE Visit (CE-PTE population) is Clinical Failure.

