6.1 Subject Disposition

The number of subjects included in each of the analysis populations defined in this SAP and the reasons for exclusion will be summarized by treatment group. A listing will be provided to indicate each subject's inclusion/exclusion from the populations, and the reason for exclusion from a population will be presented.

A list of randomized subjects who did not meet all inclusion/exclusion criteria, and which criteria were not met will be presented.

The number and percentage of subjects completing the study (defined as completing the EOT, PTE and FFU visits, as reported on CRF), as well as the completion status of EOT, PTE, and FFU visits will be presented. Reasons for not completing the study and for missing visits, as recorded on the eCRF, will be summarized (number and percentage) by treatment group for ITT, CE and PTE populations.

The number and percentage of subjects completing and prematurely discontinuing test article and the reasons for discontinuation will be presented by treatment group. A listing of all subjects who prematurely discontinued from test article or who did not complete the study will be presented, along with the primary reason for discontinuation of test article or not completing the study for ITT, micro-ITT, CE-PTE, and ME-PTE.

The number of screen failures and reason for screen failure will be presented overall. For randomized subjects, a listing will be provided that indicates the date and time of randomization, randomization number, randomized treatment assignment, drug unit identifications, and corresponding drug codes.

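### SAP 8.2 gives two overlapping compliance denominators for women who stop test article early but attend all visits; the full-course one would drop early failures that SAP 4.4 treats as evaluable

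*SAP*

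**What the plan says.** Three sentences in SAP 8.2 fix where the compliance denominator ends.

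- The last dose date is the last day on which dosing is expected, given the investigator's length of therapy, "or the actual last date the subject took test article, if s/he prematurely discontinued test article". This is the actual-last-dose rule.
- The completer rule comes next: "For subjects who complete the study, the last dose day used in the denominator calculation will be the last expected dosing day".
- A third rule covers women who terminate early: "the last day of study drug used in the denominator calculation will be the last expected dosing day before termination day".

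The full course is 56 units under Amendment 2 and 38 before it.

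The two documents define a study completer differently. SAP 6.1 goes by visits: "defined as completing the EOT, PTE and FFU visits". Protocol 10.1 also requires the regimen: "A subject will have successfully completed the study after the planned test article regimen has been administered". Protocol 8.17 does not treat women who stop drug as withdrawn: "Subjects who discontinue study treatment prematurely should complete the EOT visit, PTE visit and Final Follow-up Assessment, if possible". Under Protocol 7.14, a woman who needs other antibacterial therapy for her cystitis is a clinical failure and stops test article.

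SAP 4.4 requires all CE criteria to be met. One is that the subject "was at least 80% compliant with the dosing regimen". Another sets a dose minimum for an evaluable failure. For the once-daily omadacycline groups it reads "The subject received at least 3 doses of active test article (omadacycline groups 1, 2, and 3"; for Group 4 and nitrofurantoin it is 4 active doses. SAP 4.4 also keeps failures who took non-study antibiotics for insufficient effect, provided they meet the other CE criteria.

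**The concern.** A clinical failure who is handled as the protocol asks stops drug, attends EOT, PTE and Final Follow-up, and so meets both of the first two denominator sentences. On the actual-last-dose rule she is close to fully compliant. On the completer rule she is measured against a course that she was told to stop, and she misses 80%. The 3- or 4-dose minimum would then have no function for such a woman.

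At stake is membership of CE-EOT, CE-PTE and CE-FFU, of the ME populations drawn from CE, and of the table of subjects with at least 80% compliance. If the full-course rule is programmed, women leave CE because they failed and stopped, and an arm with more early failures loses more of them.

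**Working it through.** **Inputs.** Dosing table (Protocol 7.6, Table 2): 14 doses, each of 3 tablets and 1 capsule. Compliance = 100 × units taken / units expected (SAP 8.2). Threshold 80% (SAP 4.4).

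**The plan's own totals.** Amendment 2: 14 × 4 = 56, as stated. Before Amendment 2: 2 × 4 + 6 × (4 + 1) = 38, as stated. The superseded dosing table is not in the documents, so the split of 4 units at odd doses and 1 at even doses from Day 2 is an inference. It does give 38.

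**Threshold on the full course.** 0.80 × 56 = 44.8 units, so 12 doses (48 units) are needed.

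**A woman who takes every dose up to stopping (Amendment 2):**

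| Last dose taken | Units taken | Full course (/56) | To actual last dose, whole days | To actual last dose, by dose |
|---|---|---|---|---|
| 3 | 12 | 21.4% | 12/16 = 75.0% | 100% |
| 4 | 16 | 28.6% | 16/16 = 100% | 100% |
| 5 | 20 | 35.7% | 20/24 = 83.3% | 100% |
| 6 | 24 | 42.9% | 24/24 = 100% | 100% |
| 7 | 28 | 50.0% | 28/32 = 87.5% | 100% |
| 10 | 40 | 71.4% | 40/40 = 100% | 100% |
| 11 | 44 | 78.6% | 44/48 = 91.7% | 100% |
| 12 | 48 | 85.7% | 48/48 = 100% | 100% |

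Groups 1-3 reach 3 active doses at Dose 3; Groups 4 and 5 reach 4 at Dose 4. A failure who stops at Doses 3-11 (Groups 1-3) or 4-11 (Groups 4 and 5) therefore meets the evaluable-failure minimum but fails 80% of the full course. The evaluable-success minimums have the same problem. In Groups 1-3, 4 active doses are reached at Dose 5 (35.7%). In Groups 4 and 5, 6 are reached at Dose 6 (42.9%).

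**Before Amendment 2 (inferred split).** 0.80 × 38 = 30.4 units. Stopping at Dose 10 gives 28/38 = 73.7%, which fails. Dose 11 gives 32/38 = 84.2%, which passes.

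**Early-termination sentence.** It does not say whether termination means drug or study. Take a woman who stops after Dose 7 on Day 4. If termination means leaving the study and she leaves that day, expected units run to Day 3: 28/24 = 116.7%, and she passes. If she attends every visit and the completer sentence is used, she has 28/56 = 50.0%, and she fails.

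**Effect on a CE rate.** Assume 45 per arm (225/5, with no other CE exclusions) and 37 successes: 37/45 = 82.2%. Removing early failures:

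- 1 removed: 37/44 = 84.1%
- 2 removed: 37/43 = 86.0%
- 4 removed: 37/41 = 90.2%

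The full-course rule also removes early-stopping successes. One success removed alone gives 36/44 = 81.8%. Two of each removed gives 35/41 = 85.4%. The rate rises whenever failures make up more than 8/45 = 17.8% of those removed.

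**The case against.** The exclusion is not certain. SAP 8.2 ties the expected last day to the length of therapy that the investigator determines, so the last expected dosing day could be read as the day the investigator ended treatment. It has a specific clause for premature discontinuation of drug. Under Protocol 10.1 an early stopper is not a completer, and the visit-based definition in SAP 6.1 is a parenthesis in the disposition section. SAP 4.4 also provides for manual sponsor review before unblinding and refers to a Pathogen and CE Review Plan, which is not available here and may settle the matter. That the full-course reading empties the dose minimums suggests that it was not intended.

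These points stand as reasons not to assume the worst reading. They do not remove the overlap. SAP 1 says that the SAP prevails over the protocol, which favours the visit-based definition. The early-termination sentence does not clearly cover a woman who stopped only drug.

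A reader might infer that an inferior dose could be hidden, or that a false difference of 8 points (90.2% less 82.2%) could arise against a 10-point margin. The documents do not support either. The primary analysis is in ITT, where SAP Table 5 keeps every EOT failure as a failure. The 10-point margin is stated only for that test; CE results get nominal confidence intervals. The 8-point case assumes that half the failures stop before Dose 12, and in one arm only. SAP 6.1 also requires reasons for exclusion from each population to be summarised by treatment group, so such exclusions would be visible.

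**Conclusion.** The overlap in SAP 8.2 is real, and the SAP text does not resolve it. If the full-course denominator is applied, clinical failures who stop at or before Dose 11 under Amendment 2 leave the CE and ME populations despite meeting the evaluable-failure minimum. That SAP 4.4 means to keep them is an inference from the dose minimum and the rescue-antibiotic sentence, but a strong one: a minimum of 3 or 4 doses has no function beside 80% of 14.

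Higher CE and ME success rates are the likely direction, because failures are the women told to stop, but not a certain one. The size depends on how many stop early, which the documents do not give; the 84.1% to 90.2% range rests on the assumed 45 per arm and 37 successes. The ITT primary and micro-ITT analyses are not affected. This should be corrected, but it does not threaten the primary result.

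**What to change.** Before unblinding:

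1. In SAP 8.2, state one denominator for any subject who permanently stops test article early: expected units up to her actual last dose, whether or not she completes the visits. Count by dose, not by whole days, because whole days leave a failure who stops at Dose 3 at 75%. All others use the full course.
2. In SAP 4.4, state that for early-stopping clinical failures the evaluable-failure dose minimum governs in place of 80% of the full course.
3. State explicitly whether early-stopping successes are governed in the same way by the evaluable-success minimum. If they are, a woman in Groups 1-3 who stops after Dose 5, at 35.7% of the course, could count as an evaluable success.
4. Reconcile this text with the Pathogen and CE Review Plan.

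The cost is SAP wording and one derivation, with no new data. CE success rates may be slightly less favourable, and the 80% criterion would no longer screen out early stoppers who meet the dose minimums.

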8.3 Concomitant Medications

Medications will be coded by WHODrug Anatomical Therapeutic Chemical Classification level 3 and generic medication name. Treatments that have been administered within 7 days prior to the date of informed consent until the end of study are recorded in the eCRF.

Medications are considered concomitant if taken on or after the first dose of test article, or if their stop date is unknown or marked as continuing. Thus, in cases where a medication starts prior to the first dose, and continues throughout the treatment period, the medication will be summarized as both prior and concomitant.

All medications and significant non-drug therapies (including physical therapy and blood transfusions) administered after the subject starts treatment with test article will be listed.

Of note, summary of prior antiemetic and antibiotic medications will also be provided as described in [Section 6.5 \(Prior and Concomitant Medications\)](#).

8.4 Adverse Events

Adverse events (AEs) will be recorded and reported from signing of the informed consent form to the end of study. AEs will be coded using the MedDRA to the system organ class (SOC) and preferred term (PT) levels.

A treatment-emergent AE is defined as any AE that newly appeared or worsened in severity on or after the initiation of test article. An AE is considered treatment emergent if the AE start date and time is on or after the start date and time of the first dose of test article.

Summary tables will be provided for all treatment-emergent adverse events (TEAEs).

An overall summary of AEs will include the number of subjects who experienced at least one AE of the following categories: any AE, any TEAE, any drug-related TEAE, any severe TEAE, any serious TEAE, any drug-related serious adverse event, any serious TEAE leading to death, any TEAE leading to premature discontinuation of test article, any TEAE leading to premature discontinuation of test article and premature discontinuation from study, and any serious TEAE leading to premature discontinuation of test article.

The number and percentage of subjects reporting a TEAE in each treatment group will be tabulated by SOC and PT. The incidence of serious TEAEs, TEAEs judged to be related to test article, TEAE leading to premature discontinuation of test article and from study will be summarized by SOC and PT. Additionally, a summary by SOC, PT, and severity (mild, moderate, and severe) will be provided. For all analyses of TEAEs, if the same AE (based on PT) is reported for the same subject more than once, the AE is counted only once for that PT and at the highest severity and strongest relationship to test article.

In addition, all TEAEs, serious TEAEs, and TEAEs leading to discontinuation of test article will be provided in listings by treatment group, study site, subject, verbatim term, MedDRA SOC and PT, start and end date, seriousness flag, severity, relationship to test article, relationship to study protocol, action taken with test article, non-test article action taken and outcome.

For subjects with a TEAE of nausea or vomiting (based on the MedDRA PT), the total number of nausea and vomiting events, descriptive statistics of the study day of first onset of these events, descriptive statistics for the duration (in days) of events, and number of subjects who required anti-emetic medication will be presented by treatment group.

Listings of all AEs for treated (by treatment group) and not treated subjects will be provided indicating day relative to the first intake of the test article intake to differentiate between TEAEs and pre-therapy AEs.

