22. Need for concurrent use of uricosuric drugs (eg, probenecid, colchicine, sulfinpyrazone)
23. Use of other investigational drugs within 5 half-lives or 30 days prior to randomization, whichever is longer
24. Has previously been treated with omadacycline or previously enrolled in this study
25. Unable or unwilling, in the opinion of the investigator, to comply with the protocol requirements, or has any concomitant condition or planned medical intervention that, in the opinion of the investigator, is likely to interfere with evaluation of the response of the infection under study, determination of AEs, or completion of the expected course of treatment.

Test Article; Dose; and Mode of Administration:

- Group 1: Omadacycline 300 mg po q12h x 1 day followed by 300 mg po q24h
Group 2: Omadacycline 450 mg po q12h x 1 day followed by 300 mg po q24h
Group 3: Omadacycline 450 mg po q12h x 1 day followed by 450 mg po q24h
Group 4: Omadacycline 450 mg po q12h
Group 5: Nitrofurantoin 100 mg po q12h

Duration of Treatment:

The total duration of therapy for all subjects will be 7 days.

Pharmacokinetic Assessments

- Blood Collection (plasma);
- Urine Collection

Safety Assessments:

- Physical examinations;
- Vital signs (body weight, body temperature, blood pressure [BP], heart rate);
- Laboratory tests (Hematology, serum chemistry, urinalysis);
- AEs and Serious Adverse Events (SAEs);
- AEs of Interest (nausea and vomiting);
- Concomitant medications;
- Pregnancy assessments.

Efficacy Assessments:

- Investigator's assessment of clinical response. Clinical success is defined as resolution of signs and symptoms of the infection to the extent that further antibacterial therapy is not necessary;
- Microbiological assessment of the infection;
- Subject assessment of UTI signs and symptoms severity (via the UTI Symptoms Assessment [UTISA] questionnaire).

Statistical Methods:

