8.15.3 Assessment of Severity

The severity (or intensity) of an AE will be classified using the following criteria:

- Mild: These events are usually transient, require minimal or no treatment, and do not interfere with the subject's daily activities.
- Moderate: These events result in a low level of inconvenience or concern with the therapeutic measures. Moderate events may cause some interference with normal functioning but pose no significant or permanent risk of harm.
- Severe: These events interrupt a subject's usual daily activity and may require systemic drug therapy or other treatment. Severe events are usually incapacitating.

Changes in the severity of an AE should be documented as a new event to allow an assessment of the duration of the event at each level of intensity to be performed.

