5.1.1 Definitions

In [Table 2](#) the general definitions provided are used in the statistical analysis.

Table 2 General Definitions

Variable	Definition
Baseline	Unless otherwise stated, baseline is defined as the value closest to but prior to the initiation of test article administration.
Change from baseline	Change from baseline will be defined as the post-baseline value minus the baseline value (on a subject level). Change from baseline will only be calculated for subjects who have both baseline and at least one post-baseline value for any parameter.
Duration Variables	Duration variables will be calculated using the general formula: Duration (days) = End date - Start date + 1 If applicable, where time is collected: Duration (hh:mm) = End datetime - Start datetime
Calculated Creatinine Clearance (mL / min), Cockcroft-Gault equation	$\frac{(140 - \text{age [yrs]}) * \text{weight [kg]} * Z}{\text{Creatinine [mg/dL]} * 72}$ Z = 0.85 for Female subjects
Body Mass Index (BMI)	$\text{BMI} = \text{Weight (kg)} / \text{Height (m)}^2$

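### Nausea and vomiting event counts and durations in SAP 8.4 are built on records that Protocol 8.15.3 splits at each severity change, with no step to rejoin them

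*SAP*

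**What the plan says.** **Recording.** Protocol 8.15.3 states: "Changes in the severity of an AE should be documented as a new event". The stated purpose is to let duration be assessed separately at each level of intensity.

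**Analysis.** For subjects with treatment-emergent nausea or vomiting, SAP 8.4 plans by treatment group "the total number of nausea and vomiting events", the study day of first onset, "descriptive statistics for the duration (in days) of events", and the number of subjects who needed an anti-emetic. It plans no duration by severity level. SAP 5.1.1 (Table 2) gives the general formula "Duration (days) = End date - Start date + 1".

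**Counting rule.** The same SAP section also has a rule that begins "For all analyses of TEAEs, if the same AE (based on PT) is reported for the same subject more than once, the AE is counted". The rule then allows a single count per preferred term (PT), taken at the highest severity and strongest relationship.

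**Status of these events.** The Protocol synopsis, under Safety Assessments, names nausea and vomiting as the AEs of interest.

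Neither document defines an event for the nausea and vomiting table or says that consecutive records of one continuous episode are joined.

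**The concern.** Splitting a record at each severity change makes sense if the analysis then reports time spent at each severity. The SAP drops that analysis but keeps a count and a duration per event. The by-product of the recording rule therefore passes into the table while its purpose does not. One continuous spell of nausea that worsens and then eases can appear as three short events.

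Count and duration are this table's measures of how many episodes occurred and how long they lasted, and splitting pushes them in opposite directions: more events, each shorter. Nausea and vomiting are the listed AEs of interest, and Protocol 3.2 says the trial is meant to help select regimens for later studies. The table should therefore describe episodes, not fragments of records.

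**Working it through.** The documents state no nausea or vomiting event count or duration, so there is no planned figure to reproduce. The check applies the SAP's own formula to the Protocol's recording rule.

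**Inputs**
- Recording rule: a new event at each severity change (Protocol 8.15.3).
- Duration: end date minus start date plus 1 (SAP 5.1.1, Table 2).
- Assumed, because the documents give neither: episode length D (days) and number of severity segments k. How segment dates meet is also not stated, so both conventions are shown.

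**One episode**
- Records as collected: k events.
- Shared boundary date: the durations sum to D + (k-1), so the mean is (D+k-1)/k.
- Next-day start: the durations sum to D, so the mean is D/k.
- Joined: 1 event of D days.

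With D = 4 and k = 3 (mild, moderate, mild):
- Shared date (Days 1-2, 2-3, 3-4): (2-1+1) + (3-2+1) + (4-3+1) = 6 days over 3 events, mean 2.0.
- Next-day start: 4/3 = 1.33 days.
- Joined: 4-1+1 = 4 days, 1 event.

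For a one-day episode split within the day, each record still lasts 1 day, so only the count rises.

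**Per 10 four-day episodes, varying the share that has two severity changes (assumed)**

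| Share split in three | Events | Mean days, shared date | Mean days, next-day start |
|---|---|---|---|
| 0% | 10 | 40/10 = 4.0 | 40/10 = 4.0 |
| 10% | 9 + 3 = 12 | 42/12 = 3.5 | 40/12 = 3.3 |
| 25% | 7.5 + 7.5 = 15 | 45/15 = 3.0 | 40/15 = 2.7 |
| 50% | 5 + 15 = 20 | 50/20 = 2.5 | 40/20 = 2.0 |

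Joined, every row gives 10 events of 4.0 days.

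**The once-per-PT sentence, read literally**
- Count: each subject contributes at most one per PT, so the total only restates the numbers of subjects with each PT, which the SOC and PT tables already give. Reporting a first onset of events also presupposes that a subject can have more than one.
- Duration: the sentence settles count, severity and relationship. It does not say which start and stop dates to use when a subject has several records.

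**Outputs that do not move when a treatment-emergent episode is split**
- Subject incidence: still one subject.
- Worst severity: the maximum over the records is unchanged.
- First onset: the earliest start is unchanged.
- Anti-emetic use: a count of subjects.
- Primary analysis: uses clinical response at PTE, not AE records.

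**The case against.** The strongest reply is that the once-per-PT sentence covers all analyses of TEAEs, and the nausea and vomiting table is one of them. On its literal wording the count cannot be inflated. That stands for the count, and a reader who infers that inflated counts are certain goes further than the text. But the literal reading makes the event total redundant and leaves duration without a rule.

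Three other inferences are tempting and not supported:
- *Every change-over day is counted twice.* This needs consecutive records to share a date. Protocol 8.15.3 does not say how segments are dated, and with next-day starts nothing is counted twice.
- *The distortion is worst in particular arms.* It grows with the number of severity changes, but the documents give no data on these, overall or by arm. The blinded review in Protocol 7.4 reports nausea in about 10% of the first 145 subjects (about 15) and vomiting in one (1/145 = 0.7%), without severity. It was also used to justify adding the twice-daily 450 mg arm, so it cannot inform a comparison involving that arm.
- *Decisions to modify arms would be affected.* SAP Section 1 places the DMC interim analyses outside this SAP, and SAP 3.5 runs its analyses after the end of the study.

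It is also fair that the table is descriptive, that other tolerability outputs are intact, and that the TEAE listings carry dates and severity, so contiguous records could be found by hand. That lowers the stakes, but the table would still lack a defined unit.

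Finally, joining every same-PT record within a day of the last would be too broad. Vomiting that stops and recurs on consecutive dosing days at unchanged severity would become one long episode. This objection stands, and the joining rule below is limited accordingly.

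**Conclusion.** The concern holds in conditional form. The Protocol splits episodes at severity changes, the SAP counts and times events, and nothing rejoins the records. Summarised as collected, k segments give k events, and mean duration falls to (D+k-1)/k or D/k for any episode longer than one day. The 4-day, three-segment case has three times the count and a half or a third of the duration. The alternative literal reading gives a redundant count and an undefined duration, so the SAP needs a definition either way.

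The conflict in the text is clear. Its size in this trial is unknown, because it rests on assumed episode lengths and frequencies of severity change. A difference between arms would follow only if severity changed more often in some arms than in others. The effect is confined to the event count and duration in one descriptive safety table.

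One related edge case: AEs are recorded from consent, and SAP 8.4 sets the treatment-emergent flag by start time relative to first dosing (the rule that begins "An AE is considered treatment emergent if the AE start date and time is on or after the start date and time of the first"). Nausea present before dosing that eases afterwards would create a new post-dose record, which this rule would call treatment-emergent although nothing worsened.

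This should be corrected before the table is programmed.

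**What to change.** In SAP 8.4:

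1. Limit the once-per-PT rule to subject-incidence tables.
2. For the nausea and vomiting table, join consecutive records of the same PT in a subject when they differ in severity and the next start is on or before the previous stop + 1 day. Take the first start, last stop and highest severity, and report the number and duration of episodes.
3. Keep records of unchanged severity separate. If wanted, report days at each severity level as a separate summary, which is what Protocol 8.15.3 intended the split records for.

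Apply the joining to records already flagged as treatment-emergent, so that it does not change which records carry the flag.

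The cost is a few SAP sentences and a short programming step, with no change to data collection. The small downside is that a few truly separate adjacent episodes of different severity would be merged.
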